#### **13.1.1. Sensitivity and Supportive Analyses for the Primary Efficacy Variable**

The primary efficacy analysis will be repeated on the Per Protocol Population, if the populations are different.

#### **13.1.2. Subgroup Analyses**

The number and proportion (%) of GH responders will be presented by age categories and by octreotide responders/non-responders. Confidence intervals will only be calculated for subgroups where the sample size  $N > 2$ .

### **13.2. Secondary Efficacy Variable Analysis**

The secondary efficacy endpoint analyses will be based on the Efficacy Evaluable and on the Per Protocol population.

**Protocol code:** D-FR-10380-002

**Protocol Title:** A phase IIA, open-label, single-arm, two stage, multi-centre study to investigate the pharmacodynamics, pharmacokinetics, safety and tolerability of repeated subcutaneous administration of BIM23B065 in subjects with acromegaly

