### **5.2.5. Pharmacodynamics and Pharmacokinetics Endpoints and Evaluations**

- PD Assessments:
  - Mean serum concentration of GH over 6 hours at baseline (Day -1), Day 7 and Day 14.
  - IGF-1 levels at baseline, Day 14 and Day 28.
  - PRL levels over 6 hours at baseline, Day 7 and Day 14.
- PK Assessments:
  - Time points will follow a sparse PK sampling approach. On day 7 (first day of 1.0mg) pre-dose, 0.5h, 1h, 2h, 4h and 6h post-morning dose. On day 14 (last day of 1.0mg) pre-dose, 0.5h, 1h 2h, 4h and 6h post-morning dose.
  - One random sampling for PK analysis will also be taken at further routine study visits (Day 10) to co-ordinate with safety and PD assessments.
  - Drug (BIM23B065) and its major metabolite BIM23B133.

**Protocol code:** D-FR-10380-002

**Protocol Title:** A phase IIA, open-label, single-arm, two stage, multi-centre study to investigate the pharmacodynamics, pharmacokinetics, safety and tolerability of repeated subcutaneous administration of BIM23B065 in subjects with acromegaly

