### **9. ANALYSIS POPULATIONS**

The following populations will be used during statistical analyses:

- Safety population/Intent to treat (ITT): All subjects with at least one IMP administration
- Modified Intent to treat (mITT) population: All subjects in the Safety population with available pharmacodynamic data and no protocol deviations with relevant impact on PD data.

**Protocol code:** D-FR-10380-002

**Protocol Title:** A phase IIA, open-label, single-arm, two stage, multi-centre study to investigate the pharmacodynamics, pharmacokinetics, safety and tolerability of repeated subcutaneous administration of BIM23B065 in subjects with acromegaly

- Efficacy Evaluable (EE) population: All subjects in the mITT population with an evaluable primary efficacy endpoint (mean concentration of GH over 6 hours) at baseline and V8 (+14 days post baseline).
- Per protocol (PP) population: All subjects in the efficacy evaluable (EE) population who complete the study and for whom no major protocol violations/deviations occurred.

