### **13.2.1. GH responders**

The following secondary GH response criteria will be defined on Day 7 and Day 14 based on the GH profiles:

- Mean GH  $\leq$  1.0 ug/l
- Mean GH  $\leq$  2.5 ug/l
- Mean GH reduction from baseline  $\geq$  50%

The GH measurements, their mean by visit, the mean percent changes from baseline and the various GH responder criteria will be listed by patient and visit. The number and proportion (90% CI calculated by the Clopper-Pearson method) of GH responders on Day 7 and Day14 will be reported.

Descriptive summaries will be presented for the measured GH values and for the calculated percent changes from baseline. Mean (+ SE) profiles over time will be displayed graphically.

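### Read literally, the SAP computes Day 7 GH responder rates only in subjects who also have a Day 14 GH profile, which leaves out those who withdraw on Days 8-13

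*SAP*

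**What the plan says.** - **Population for secondary efficacy.** SAP 13.2: "The secondary efficacy endpoint analyses will be based on the Efficacy Evaluable and on the Per Protocol population". The table in 9.1 agrees: secondary efficacy endpoints are ticked for EE and PP only.
- **Time points.** SAP 13.2.1: "The following secondary GH response criteria will be defined on Day 7 and Day 14 based on the GH profiles". The criteria are mean GH at or below 1.0 µg/l, mean GH at or below 2.5 µg/l, and a reduction of at least 50%. The number and proportion, with a 90% Clopper-Pearson interval, "of GH responders on Day 7 and Day14 will be reported". No other population is named there.
- **EE.** SAP 9: "All subjects in the mITT population with an evaluable primary efficacy endpoint (mean concentration of GH over 6 hours) at baseline and V8", where V8 is the Day 14 visit.
- **PP.** SAP 9: "All subjects in the efficacy evaluable (EE) population who complete the study and for whom no major protocol violations/deviations occurred". It is a subset of EE.
- **mITT.** SAP 9: "All subjects in the Safety population with available pharmacodynamic data and no protocol deviations with relevant impact on PD data". No Day 14 value is required.
- **PD assessments.** SAP 5.2.5 lists "Mean serum concentration of GH over 6 hours at baseline (Day -1), Day 7 and Day 14" as a PD assessment, and the 9.1 table assigns PD assessments to mITT and EE. Section 13.2.2 names mITT for the IGF-1 and PRL summaries.
- **Missing data and replacement.** The section on methods for missing data (the second section numbered 10.1) adopts observed cases without substitution. It excludes safety and tolerability withdrawals from replacement. Other withdrawals are replaced until 12 evaluable subjects have completed Visit 8.

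**The concern.** The Day 7 criteria need only the Day -1 and Day 7 profiles. Using EE or PP selects the Day 7 denominator on something that happens a week later, the presence of a Day 14 profile. No imputation is involved, because the Day 7 value has been measured. Dropping it because another visit is missing fits badly with the SAP's own observed-case approach.

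Day 7 is the first day at the 1.0 mg dose and the only scheduled post-baseline GH profile before Day 14. It is therefore the only time point at which the GH response of subjects who leave on Days 8-13 can be summarised. If leaving is related to response or tolerability, the tabulated Day 7 rate describes those who stayed rather than those measured on that day. With at most 12 evaluable subjects per stage, one or two subjects visibly move the percentage.

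**Working it through.** **1. The plan's own figure.** SAP 8 gives over 84% power for 12 evaluable subjects, null rate 33%, alternative 75%, one-sided 0.05, exact test. With X ~ Bin(12, p):
- Cut-off 7: P(X ≥ 7 | 0.33) = 0.0632, above 0.05.
- Cut-off 8: P(X ≥ 8 | 0.33) = 0.0176, and power P(X ≥ 8 | 0.75) = 0.8424.

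The figure is reproduced. It concerns Day 14 response in evaluable subjects, so the point made here does not touch it.

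**2. Who enters the Day 7 rate.** Take a dosed subject with evaluable Day -1 and Day 7 profiles, no deviation affecting PD data, and withdrawal on one of Days 8-13.
- mITT: included, since PD data are available.
- EE: excluded, since there is no Day 14 profile.
- PP: excluded, since PP lies within EE.
- Day 7 responder proportion under 13.2 and 13.2.1: computed on EE and PP, so the subject is not counted.

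**3. Size.** The SAP states no withdrawal rate. The number who leave, and how many of them responded at Day 7, are assumptions, so the full range is shown. Suppose n subjects have Day 7 profiles, x of them respond, k leave before Day 14 without replacement, and j of those k were responders. Then:
- Rate on all observed Day 7 data = x/n
- Rate on EE = (x − j)/(n − k)
- 90% Clopper-Pearson limits for r responders of m: lower = 5th percentile of Beta(r, m − r + 1); upper = 95th percentile of Beta(r + 1, m − r)

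*Case A, losses not replaced (safety or tolerability).* n = 12, x = 8. All observed Day 7 data give 8/12 = 66.7% (90% CI 39.1-87.7).

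| k lost | EE rate if all k were responders | EE rate if none were |
|---|---|---|
| 1 | 7/11 = 63.6% (35.0-86.5) | 8/11 = 72.7% (43.6-92.1) |
| 2 | 6/10 = 60.0% (30.4-85.0) | 8/10 = 80.0% (49.3-96.3) |
| 3 | 5/9 = 55.6% (25.1-83.1) | 8/9 = 88.9% (57.1-99.4) |

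*Case B, losses replaced up to 12 evaluable.* Suppose EE shows 8/12 = 66.7% at Day 7 and two replaced subjects also had Day 7 profiles. All observed data then give between 8/14 = 57.1% (32.5-79.4) and 10/14 = 71.4% (46.0-89.6).

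The direction depends on whether those who left were responders. With no withdrawals on Days 8-13, nothing changes.

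**The case against.** Four arguments favour leaving the plan as it is.

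- **The data are not lost.** Section 13.2.1 lists GH values, means, percent changes and responder status by patient and visit, and 11.1 lists withdrawn subjects with reason and date. A reader might infer that the plan discards these responses or hides whether those who left were responding. The documents do not support that: only the tabulated count, proportion and interval are affected. This stands.
- **Part of the mITT reporting may already be there.** Sections 5.2.5 and 9.1 together allow the Day 7 GH descriptive summaries to be read as mITT. This stands for the summaries. It does not rescue the responder proportions, because 13.2.1 sits under the EE/PP statement and has no override of the kind 13.2.2 has for IGF-1 and PRL.
- **Nothing is decided on Day 7.** Day 7 response is not among the secondary endpoints in 5.2.2, carries no hypothesis, and enters neither the interim rules nor the sample size. A reader might infer that the efficacy conclusion is biased, but the primary test and the stopping rules use Day 14. This stands and limits the weight of the point.
- **Large shifts need particular circumstances.** An example such as 7/9 = 78% on EE (45-96%) against 7/12 = 58% on all observed data (32-82%) needs three unreplaced losses after Day 7, so for safety or tolerability under the replacement rule, and no responder among them. The intervals overlap heavily, and the direction reverses if those three responded.

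A common denominator on Days 7 and 14 is also a legitimate way to show change within the same subjects. That supports keeping an EE display at Day 7, but not making it the only one.

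**Conclusion.** The point holds as a limited one. Taken literally, 13.2, 13.2.1 and 9 together remove subjects with measured Day 7 responses from the Day 7 responder rate because of a later event, even though the SAP adopts observed cases and already defines a population that would keep them. Because safety and tolerability withdrawals are not replaced, the loss can be selective.

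The size rests on assumed withdrawals. With 8/12 Day 7 responders, the rate moves by a few percentage points for one unreplaced loss and, at the extremes, from 67% down to 56% or up to 89% for three. The consequence is confined to a descriptive secondary table. It is worth correcting because the change is cheap, not because any conclusion of the trial depends on it.

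**What to change.** In 13.2.1:

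1. Report Day 7 responder counts, proportions and 90% intervals on all mITT subjects with evaluable Day -1 and Day 7 GH profiles.
2. Confirm that the Day 7 GH descriptive summaries follow the mITT assignment for PD assessments in 9.1.
3. Keep EE and PP for Day 14, and show EE at Day 7 as supportive for the within-subject comparison with Day 14.
4. Print n for each day, and add a note to the 9.1 table so that it agrees.

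The cost is a sentence or two, one table population and a note. No new data or imputation are needed. The drawback is that the Day 7 and Day 14 rates will have different denominators; the printed n and the supportive EE display deal with that.

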### **13.2.1. GH responders**

The following secondary GH response criteria will be defined on Day 7 and Day 14 based on the GH profiles:

- Mean GH  $\leq$  1.0 ug/l
- Mean GH  $\leq$  2.5 ug/l
- Mean GH reduction from baseline  $\geq$  50%

The GH measurements, their mean by visit, the mean percent changes from baseline and the various GH responder criteria will be listed by patient and visit. The number and proportion (90% CI calculated by the Clopper-Pearson method) of GH responders on Day 7 and Day14 will be reported.

Descriptive summaries will be presented for the measured GH values and for the calculated percent changes from baseline. Mean (+ SE) profiles over time will be displayed graphically.

### **13.2.2. PD endpoints**

The IGF-1 and PRL measurements and the mean of the PRL concentration will be listed by patients and by visits along their change from baseline in percent.

Descriptive summaries will be presented for the measured concentration values and for the calculated percent change from baseline in the mITT set. Mean (+ SE) profiles over time will be displayed graphically.

The number and proportion (%) of subjects with IGF-1 < age normalized ULN, will be presented by visit along with the 90% Clopper-Pearson CI.

## **14. SAFETY AND TOLERABILITY ANALYSES**

The safety analyses will be performed based upon the ITT population.

### **14.1. Adverse Events**

Adverse events will be coded using the Medical Dictionary for Regulatory Activities (MedDRA) central coding dictionary, version 19.1 or higher version.

**Protocol code:** D-FR-10380-002

**Protocol Title:** A phase IIA, open-label, single-arm, two stage, multi-centre study to investigate the pharmacodynamics, pharmacokinetics, safety and tolerability of repeated subcutaneous administration of BIM23B065 in subjects with acromegaly

Only treatment-emergent AEs (i.e. AEs which occurred or worsened in severity during or after the first administration of a study drug) will be presented in tables. AEs occurred before the first administration of the study drug will be listed separately.

#### **14.1.1. Summary of AEs**

An overview AE summary table will be prepared presenting the number and proportion of subjects in the following categories:

- subjects reporting any adverse events
- subjects with Serious AEs (SAEs)
- deaths
- subjects with AEs leading to early withdrawal
- subject with severe AEs
- subjects with IMP-related AEs

A data listing of SAEs will be provided, displaying details of the event(s) captured on the eCRF. Serious adverse event narratives will be written by Accelsiors PV team and reviewed then by Aepodia S.A. and Ipsen Pharma SAS prior to be inserted in the CSR.

#### **14.1.2. Deaths**

The details of the event(s) captured on the eCRF will be supplied and narratives will be written by Accelsiors PV team and reviewed the by Aepodia S.A. and Ipsen Pharma SAS.

#### **14.1.3. AE listings**

All treatment-emergent AEs (TEAEs) will be listed by subject ID, presenting the start and end date of AE, the duration, as well as the period in which it occurred (titration/treatment), the last dose received prior to AE occurrence, classification by SOC and PT, severity, outcome, concomitant treatment, relationship to study medication (i.e. related or not related) and action taken.

AEs occurred before the first study drug administration will be listed separately.

A listing of AEs leading to withdrawal, SAEs, deaths will be provided, displaying details of the event(s) captured on the eCRF.

#### **14.1.4. AE tables**

Summary tables of number of subjects with TEAEs will be provided by PT in decreasing frequency, by SOC and PT and by SOC, PT and maximum severity. If a patient experiences more

**Protocol code:** D-FR-10380-002

**Protocol Title:** A phase IIA, open-label, single-arm, two stage, multi-centre study to investigate the pharmacodynamics, pharmacokinetics, safety and tolerability of repeated subcutaneous administration of BIM23B065 in subjects with acromegaly

than one AE within a preferred term, only the AE with the greatest intensity will be included in the summaries.

## **14.2. Cardiovascular Vital Signs**

### **14.2.1. Blood Pressure and Heart Rate**

All available measurements (i.e. systolic blood pressure, diastolic blood pressure and heart rate) will be listed with visit days and time-points. Abnormal values will be marked by bolding. The normality range for systolic blood pressure is 100-140mmHg, for diastolic blood pressure 60-90mmHg and for the heart rate from blood pressure measurements 60-100mmHg (inclusive of the borders).

The time-matched change from baseline will be calculated for all post-baseline scheduled measurements after D1 T0 that has corresponding measurement at the same time point on Day -1.

Descriptive statistics (n, mean, SD, median, minimum and maximum) will be provided for the scheduled values and changes from baseline at each time point.

### **14.2.2. Orthostatic hypotonia**

The diagnosis of orthostatic hypotension can be set if there is a decrease between the measurement in a supine position and standing position of  $\geq 20$  mmHg in SBP or a  $\geq 10$  mmHg in DBP or an increase  $\geq 30$  bpm in heart rate. By patient listing will be provided with the measurement pairs (supine – standing), the position how they were measured, the calculated difference between the supine and standing measurement. The values will be flagged if any criteria of orthostatic hypotonia was fulfilled.

Frequency tables will be created to present the proportion of subjects with orthostatic hypotension by visit, for each time point and overall. The number and proportion of orthostatic hypotension episodes will be summarized by visit.

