### 5.1.2. Secondary Objectives

- To assess the safety and tolerability of repeated administration of BIM23B065 in subjects with acromegaly.
- To assess the pharmacokinetics (PK) and PD of repeated administration of BIM23B065.
- To investigate the PK of BIM23B133 which is the major metabolite of BIM23B065.
- To assess the correlation of BIM23B065 exposure with blood pressure (BP) and heart rate (HR).

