### 10.2. Definition of Baseline

Most baseline assessments will be performed on Day -1 (Visit 3) with some exceptions. In case the data of the planned baseline assessment is not available, the last assessment which precedes the first administration of the IMP will be used as a baseline.

*Statistical Analysis Plan*

*SD-BS-014, version 1.0*

*Parent document: SOP-BS-005*

**Protocol code:** D-FR-10380-002

**Protocol Title:** A phase IIA, open-label, single-arm, two stage, multi-centre study to investigate the pharmacodynamics, pharmacokinetics, safety and tolerability of repeated subcutaneous administration of BIM23B065 in subjects with acromegaly

- For the GH and PRL calculations the mean serum concentration will be used as baseline, collected over 6 hours on the Day -1. The baseline IGF-1 will be measured on Day -1.
- For antibodies anti-BIM23B065 the baseline will be the serum concentration taken prior to octreotide test dose, on V2.
- For other laboratory assessments (all endocrine and clinical laboratory assessments, parameters of glucose metabolism etc.) baseline will be the measurement of Day -1. At the parameters of glucose metabolism more baseline values will be used in accordance to the fasting condition or the relative time from meals (the fasting condition on Day -1 will be compared with the fasting condition of the studied day, while the assessment one hour after meal will be compared to the baseline (Day -1) one hour after meal measurement etc.).
- For BP and HR, orthostatic hypotonia, and ECG, the baseline will be the corresponding measurements on Day -1 at the same time points (i.e. time-matched). For Holter the baseline will be the assessment on Day -1.
- For gallbladder echography, the baseline will be the assessment during the screening period.
- For other results of the physical examination (body weight, body temperature etc.) the D-1 assessments will be the baseline.

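### The orthostatic hypotension rate pools heart-rate-only positives with blood-pressure falls, leaves 'overall' undefined and does not use the Day -1 baseline, so it is not a treatment-emergent rate of hypotension

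*SAP*

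**What the plan says.** SAP Section 14.2.2 opens with "The diagnosis of orthostatic hypotension can be set if there is a decrease between the measurement in a supine position and standing position" of at least 20 mmHg in systolic pressure or at least 10 "mmHg in DBP or an increase" of at least 30 bpm in heart rate. One criterion is enough: "The values will be flagged if any criteria of orthostatic hypotonia was fulfilled".

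Two summaries follow, both under the hypotension label:

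- At subject level: "Frequency tables will be created to present the proportion of subjects with orthostatic hypotension by visit, for each time point and overall".
- At episode level: "The number and proportion of orthostatic hypotension episodes will be summarized by visit".

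Neither is split by criterion, and 'overall' is not explained.

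Section 10.2 sets a baseline for this variable: "For BP and HR, orthostatic hypotonia, and ECG, the baseline will be the corresponding measurements on Day -1 at the same time points". Section 14.2.2 does not refer to it. It plans no change from baseline, no shift table and no count of new cases.

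**The concern.** Three things combine in the same table.

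1. **Label and content differ.** The row is called orthostatic hypotension, but a subject whose pressure holds or rises on standing enters it if heart rate goes up by 30 bpm. No separate count is planned.
2. **'Overall' has no stated scope.** It may span all visits, possibly with Day -1, or only the time points within one visit.
3. **The baseline is declared but not applied.** The trial is open-label with no control group, so the subject's own Day -1 reading is the only reference for an orthostatic response that was present before dosing.

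The overall proportion is the figure most likely to be carried into a safety summary. A reader would naturally take it as the share of subjects who became hypotensive on standing while on treatment, and the table as specified does not give that number.

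**Working it through.** The SAP states no orthostatic rate, threshold or power, so there is no figure of its own to reproduce. The check is one of logic, followed by the possible size.

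**Step 1: direction.** Let A be the subjects meeting any criterion at any reading, and B the subjects meeting a blood-pressure criterion at a reading after first dose. Every member of B is in A, so |A|/N ≥ |B|/N. The inequality is strict only if at least one subject is positive solely through heart rate or solely before dosing. Otherwise the excess is 0.

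**Step 2: both readings of 'overall'.**

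- *Across all visits:* the figure is A if Day -1 is included. If Day -1 is excluded, it still contains the heart-rate-only positives.
- *Within each visit:* Day -1 is kept apart, but the SAP then has no subject-level rate over the treatment period. By-visit counts cannot be summed to one, because a subject may be positive at several visits. As an illustration with assumed counts, 2 positive subjects at each of three dosing visits could be as few as 2 or as many as 6 distinct subjects.

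Neither reading yields B.

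**Step 3: comparison with neighbouring sections.**

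| SAP section | How pre-dose status is handled |
|---|---|
| 14.1 Adverse events | Tables limited to treatment-emergent events |
| 14.2.1 Blood pressure and heart rate | Time-matched change, for measurements after D1 T0 |
| 14.2.3 12-lead ECG | Change from two defined baselines |
| 14.2.4 Holter | Shift table from baseline |
| 14.2.2 Orthostatic hypotonia | Baseline set in 10.2, no use stated |

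**Step 4: weight of one subject.** The contribution is 1/N.

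- N = 12 (the evaluable target per stage in Section 8): 1/12 = 8.3 points; two subjects, 2/12 = 16.7; three, 3/12 = 25.0.
- N = 8: 1/8 = 12.5 points. N = 6: 1/6 = 16.7 points. These are the interim looks in Section 7.2 at which a regimen may stop.
- Safety tables use everyone dosed (Sections 9 and 14), so replacements can take N above 12 and the weight below 8.3 points.

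**Step 5: illustration with assumed inputs.** The SAP gives no event rates and no number of supine-standing pairs. Assume independent pairs, 20 after dosing and 4 before, each with a 2% chance of meeting a blood-pressure criterion. The chance that a subject is positive at least once is 1 − (1 − p)^n:

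- blood pressure only, post-dose: 1 − 0.98^20 = 33.2%
- blood pressure only, all 24 pairs: 1 − 0.98^24 = 38.4%
- with a further 1% heart-rate-only chance per pair, all 24 pairs: 1 − 0.97^24 = 51.9%

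The gap between first and last is 51.9 − 33.2 = 18.7 points. With no pre-dose pairs pooled and no heart-rate-only cases it is 0. These figures show how repeated readings build up the subject-level rate; they do not predict this trial.

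**The case against.** The best defence is that the table is descriptive. Section 14.2.2 does not call the rate drug-related or treatment-emergent, tests nothing, and feeds none of the counted stopping rules in Section 7.2, which use GH responders and protocol-defined dose-limiting toxicities. Drug relationship is handled under adverse events. The heart-rate criterion is openly part of the definition, and whether it belongs there is a clinical choice that may come from the protocol. Day -1 has its own visit label (Section 10.3), so by-visit tables already show it separately. The listing gives each supine-standing pair with its difference, and Section 14.2.1 summarises systolic pressure, diastolic pressure and heart rate separately.

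Most of this stands, and it rules out three stronger readings that a reader might infer:

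- *That the rate overstates drug-related hypotension.* The SAP makes no such attribution, and any excess depends on cases that may not occur.
- *That Day -1 episodes are counted in 'overall'.* The word is undefined. The text does not show that they are.
- *That the secondary objective on exposure and blood pressure or heart rate is compromised.* PK/PD analysis is assigned to a separate pharmacometric plan, and nothing makes this table the vehicle for that objective.

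The defence does not supply the missing count. The listing allows someone to rebuild it by hand, but the by-visit tables do not. The summaries in Section 14.2.1 describe the measurements and their changes, not how many subjects met a postural criterion.

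**Conclusion.** The point holds as a minor reporting fault. As written, Section 14.2.2 gives one pooled rate under a blood-pressure label, with an undefined overall scope and no stated use of the baseline set in Section 10.2. The overall proportion cannot be read as a treatment-emergent rate of hypotension. If it spans visits, it can equal or exceed that rate but cannot fall below it. If it is per visit, no such rate is produced.

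The size cannot be derived from the SAP and may be zero. The 8.3 points per subject assumes a denominator of exactly 12, which is not fixed. The percentages in Step 5 rest entirely on assumed inputs. The primary analysis and the stated interim decision counts are not affected.

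**What to change.** Leave the three criteria and the combined flag as they are, and change only the tabulation in Section 14.2.2:

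1. **Separate rows.** Beside the combined row, show subjects meeting a blood-pressure criterion (systolic or diastolic) and subjects meeting only the heart-rate criterion. State the hierarchy, so that a subject meeting both, at the same or different readings, is counted in the blood-pressure row. Apply the same split to the episode summary.
2. **Define 'overall'.** State that it means any reading after first dose, each subject counted once, with Day -1 in its own column.
3. **Use the baseline.** Add the number of subjects newly positive relative to the time-matched Day -1 reading. State how post-dose readings without a Day -1 counterpart are treated; Section 14.2.1 already restricts its time-matched changes to readings that have one.
4. **State the denominator** beside each proportion, since it need not be 12.

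The cost is a few extra rows and one column in an existing table, from data already listed. No new assessment and no change of clinical criterion is involved.

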#### 10.1. Methods for Missing Data

A subject is considered evaluable if he or she completes the 14-day treatment period (with 6 hours GH samples collected). Subjects who withdraw from the study before reaching the point of being evaluable may be replaced. If the withdrawal is due to safety and tolerability reasons no replacement will be performed, but otherwise the subject will be replaced. If 12 evaluable subjects have already completed visit 8 (day 14) any subsequent withdrawn subjects will not be replaced.

A minimum of 8 octreotide responders must be evaluable in the final analysis. If an octreotide responder withdraws prematurely, he/she will be replaced by another octreotide responder. If an octreotide non-responder withdraws, they can be replaced by either a responder or non-responder.

No substitution of missing values will be performed, an observed case approach will be used.

In all listings, missing or incomplete dates will be left as they have been recorded. However, for calculation / sorting / assignation based on dates, the following methods will be used:

- The most conservative approach will be systematically considered. For example, if the onset date of an AE/concomitant medication is missing / incomplete, it is assumed to have occurred during the study treatment phase (i.e. a TEAE for AEs) except if the partial onset date or other data (e.g. stop date) indicates differently.
- A missing/incomplete date of medical history or disease diagnosis will be assumed to have occurred before any study treatment.

Where this is possible, the derivations based on a partial date will be presented as superior inequalities (i.e.: for an AE started in FEB2004 after the administration performed on

**Protocol code:** D-FR-10380-002

**Protocol Title:** A phase IIA, open-label, single-arm, two stage, multi-centre study to investigate the pharmacodynamics, pharmacokinetics, safety and tolerability of repeated subcutaneous administration of BIM23B065 in subjects with acromegaly

31JAN2004, the days since last dose will be “≥2”, similarly the duration of ongoing AEs or medication will be “≥xx” according to the start and last visit dates).

If the severity or the relationship to the IMP is not available for an AE it will be marked as ‘unknown’.

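### Orthostatic hypotension table: a standing reading prevented by symptoms is not counted at its time point, so the rate is biased low if such readings occur

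*SAP*

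**What the plan says.** SAP Section 14.2.2 (Orthostatic hypotonia) opens its case definition with "The diagnosis of orthostatic hypotension can be set if there is a decrease between the measurement in a supine position and standing position of" and then sets the thresholds: at least 20 mmHg systolic or at least 10 mmHg diastolic, with a heart rate rise of at least 30 bpm as a further alternative. The by-patient listing shows the supine and standing pairs and "the calculated difference between the supine and standing measurement". The flag follows from these numbers: "The values will be flagged if any criteria of orthostatic hypotonia was fulfilled".

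Two summaries are built on the flag:
- By subject: "Frequency tables will be created to present the proportion of subjects with orthostatic hypotension by visit, for each time point and overall".
- By episode: "The number and proportion of orthostatic hypotension episodes will be summarized by visit".

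Neither has a stated denominator. The section does not say what happens when a standing reading is not obtained.

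The general rule is in the section titled Methods for Missing Data (the second of two sections numbered 10.1): "No substitution of missing values will be performed, an observed case approach will be used". It makes no exception for safety variables. The analysis set comes from Section 14: "The safety analyses will be performed based upon the ITT population".

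**The concern.** All three criteria compare a standing value with a supine one. A subject who becomes faint on standing and lies down before the measurement has no standing value, so no criterion can be met. Under the observed-case rule the subject then either drops out of the denominator or stays in it as a non-case; the SAP does not say which.

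This differs from ordinary missing vital signs. A standing reading can be missing because of the postural event that the table is meant to count, so missingness depends on the outcome. The result is then a downward bias and not only a loss of precision.

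Safety and tolerability form a secondary objective (Section 5.1.2), and supine and standing blood pressure and heart rate are a named safety endpoint (Section 5.2.4). The orthostatic table is the summary that a reader would consult for this effect. With about a dozen subjects per regimen, one uncounted subject changes the figure visibly.

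**Working it through.** The SAP states no expected orthostatic hypotension rate and no expected number of incomplete standing tests, so there is no figure of its own to reproduce.

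**Inputs**
- Case definition, flag and summaries: SAP Section 14.2.2.
- No substitution, observed cases: SAP Section 10.1, Methods for Missing Data.
- N = 12: the evaluable subjects per stage in SAP Section 8, borrowed for scale only. The table uses the ITT set, whose size may differ.
- c, subjects flagged at a time point on a completed pair: assumed, 1 to 3.
- m, subjects whose standing reading was prevented by orthostatic symptoms at that time point: assumed, 0 to 3.

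**Formulas, at one time point**
- Completed pairs only: c / (N − m)
- All subjects in the denominator, missing treated as non-case: c / N
- Symptom-prevented readings counted as cases: (c + m) / N

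**Direction.** c/N is below (c + m)/N whenever m > 0. For the completed-pairs version, c/(N − m) < (c + m)/N is equivalent to cN < (c + m)(N − m), that is, 0 < m(N − m − c). This holds whenever m > 0 and at least one completer is not a case. Outside that corner, either reading of the denominator understates.

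**Size, N = 12 and c = 2**

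| m | c/(N − m) | c/N | (c + m)/N | Shortfall, points |
|---|---|---|---|---|
| 0 | 2/12 = 16.7% | 16.7% | 16.7% | 0 |
| 1 | 2/11 = 18.2% | 16.7% | 3/12 = 25.0% | 6.8 to 8.3 |
| 2 | 2/10 = 20.0% | 16.7% | 4/12 = 33.3% | 13.3 to 16.7 |
| 3 | 2/9 = 22.2% | 16.7% | 5/12 = 41.7% | 19.4 to 25.0 |

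With m = 1 and other values of c:
- c = 1: 9.1% or 8.3%, against 16.7%.
- c = 3: 27.3% or 25.0%, against 33.3%.

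So one aborted test costs about 6 to 8 points over this range. With both stages pooled at N = 24, c = 2 and m = 1, the figures are 8.7% or 8.3% against 12.5%, a shortfall of about 4 points.

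**Visit and overall rows.** A subject missed at one time point is still counted there if another completed pair is positive. If each of k other pairs is independently positive with probability q (assumed), the chance of still being counted is 1 − (1 − q)^k. For k = 3 this is 27% at q = 0.1, 66% at q = 0.3 and 88% at q = 0.5. These rows are therefore less affected than the time-point rows. The episode count has no such recovery: a test that yields no standing value cannot enter it as an episode.

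**The case against.** The case for leaving the section alone has real force.

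- A reader might infer that such a subject can never be a case. The SAP does not support that: another positive pair still counts the subject in the visit or overall row. The criteria are also alternatives, so a standing heart rate alone can flag a subject whose standing blood pressure was not obtained.
- A reader might infer that the reported rate is biased low as a matter of fact. Nothing in the SAP shows that standing readings will be missed or why, and with none missed the result is unchanged.
- The restriction to completed pairs is inferred from Sections 14.2.2 and 10.1 together; neither states it.
- The events need not vanish from the report. Section 14.1.3 lists every treatment-emergent event with severity, last dose and action taken, and Section 14.1.4 adds "Summary tables of number of subjects with TEAEs will be provided by PT in decreasing frequency". The by-patient listing of pairs may also show an absent standing value.
- The exposure and blood pressure objective cannot be used to raise the stakes, because that analysis sits in the separate Pharmacometric Analysis Plan. Nor does the SAP say that postural effects are expected: its titration hold refers to cardiovascular events in general, and the monthly report does not mention supine-standing differences.
- Counting symptoms as cases mixes a symptom with a measured definition, and dizziness has other causes. The SAP mentions a reason for not doing an assessment only for the physical examination.

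Most of this stands and limits the point. It does not remove it: at the affected time point no criterion can be met without a standing value, Section 10.1 gives no exception, and nothing links the adverse event tables to the orthostatic table. The last objection is a reason to show the symptom-based count as a supportive line and not as a replacement.

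**Conclusion.** The point holds in conditional form. As the SAP is written, a subject with no standing reading because of orthostatic symptoms is not counted at that time point, and is counted at the visit or overall only through another positive pair. If such readings occur, the time-point and episode rates are understated. In the illustration one aborted test among 12 subjects gives 17 to 18% against 25%; if there are none, nothing changes.

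The size rests wholly on assumed counts, and on treating a symptom-prevented reading as a true case. A broader conclusion, that the plan hides postural events or makes the drug look safer overall, is not supported: the effect is confined to one descriptive table, the symptoms may be reported as adverse events, and the GH analysis is untouched. The protocol, which may say how an aborted standing test is recorded, is not at hand. The case flag and the denominator are nevertheless analysis rules that belong in this SAP.

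**What to change.** Amend SAP Section 14.2.2 as follows:

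1. Keep the pair-only proportion and state its denominator: subjects with a completed supine and standing pair at that time point. State the denominators of the visit, overall and episode summaries too, and say how a test with only one of standing blood pressure and heart rate is treated.
2. Add a row with the number of standing readings not obtained. Within it, separate those with concurrent orthostatic symptoms, identified from a concurrent adverse event, or from a recorded reason if the CRF collects one.
3. Add a supportive proportion that counts those symptomatic subjects as cases, over all subjects due for the assessment. State that the observed-case rule of Section 10.1 does not apply to this line.

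The cost is SAP wording, one derived flag and two extra table lines. No planned result is replaced, and if no standing reading is missed the two proportions coincide. There are two small downsides. Attributing a missed reading to symptoms is somewhat subjective. Readings missed for unrelated reasons also stay in the supportive denominator as non-cases. The separate row makes both visible.
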